**Research Objectives / Specific Aims / Outcome Measures:**

**Objective:** To determine if debridement improves healing time for secondary intention wounds.

**Hypothesis** Aggressive and frequent debridement of an acute post-surgical wound shortens healing time.

**Outcomes Measures** The primary outcome measure will be time to healing. Secondary outcomes will include patient satisfaction with their scar (as assessed by the Patient Scar Assessment Questionnaire) at time of complete healing, cosmetic appearance (Visual analog Scale) as rated by a blinded reviewer at time of complete healing, number of required debridements by time of complete healing, treatment failures at week 16, and number of complications (including pain, bleeding, infection, tumor recurrence) by time of complete healing or by week 16.

The Patient Scar Assessment Questionnaire is a validated questionnaire used standardly in Dermatology for assessing patient-based outcome measures of scarring. It consists of 5 subscales: appearance, symptoms consciousness, satisfaction with appearance and satisfaction with symptoms. Each subscale consists of a set of items with 4-point categorical responses, scoring 1 to 4 points (with 1 point assigned to the most favorable category and 4 assigned to the least favorable). It has been demonstrated to be a reliable and valid measure of patients' perception of scarring.

The Visual Analog Scale is a validated image-based scale that is frequently used in the Dermatology and Plastic Surgery literature, that uses

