**Notes:**

- The following information will be recorded for each patient at each clinic visit for both treatment arms, using a standardized data collection form: Date of follow up; pain (0/10); episodes of bleeding (# and whether mild, moderate, or severe); amount of crust (mild, moderate, or severe); amount of fibrin (mild, moderate, or severe); size

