**Statistical Issues**

Sample Size/Power	Time to healing will be the primary outcome measure and will be compared between groups using a two-sided t-test. There is limited literature regarding similar patients to help guide estimates for a power analysis. Based on a review of the literature,  and a brief review of patients previously seen at our clinic, we powered the study to detect a difference in healing time between treatment groups of 14 days, and assumed a standard deviation (SD) of 15 days. To obtain 80% power to detect such a difference, assuming alpha=0.05 and a two-sided t-test, 20 patients per group (40 total) are required.
Anticipated Strengths	We performed a priori power analysis. We are using a randomized study design with validated survey instruments. We plan to use a blinded reviewer of the final cosmetic outcome.
Anticipated Limitations	Given the nature of our study, it will not be possible to conceal treatment arm to patients or providers, though assessment of the final outcome will be by blinded reviewer. If variability in wound healing is greater than anticipated, we may not have statistical power to detect differences between groups; however, the estimates we obtain will help inform future studies. The minimal debridement group will be seen by the clinician every two weeks; while the aggressive debridement group will be seen weekly. It is therefore possible that ascertainment of time to wound healing will differ between groups. However, we hope to avoid this bias checking with the minimal debridement group by phone on weeks where they have no scheduled visit.

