**Potential Risks and Discomforts:**

The probability and magnitude of harm or discomfort anticipated in the research are not greater in and of themselves than those ordinarily encountered during routine post-operative care, including the performance of routine physical or psychological examinations or tests. However, since this study is comparing two methods of treating post-surgical wounds, it is possible that one treatment method is significantly more effective than another. By participating in this study, there is the risk that the patients randomized to the less effective treatment method may delay their wound healing. It is also possible that one group of patients may have more side effects than the other. For example, patients in the aggressive debridement group may experience more bleeding, pain, and scarring than the minimal debridement group.

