**Statistical Analysis:**

Analytic Plan

Differences in demographic and wound characteristics between groups will be compared to evaluate balance between groups. Differences between treatments arms for the primary (time-to-healing) and continuous secondary outcomes (patient satisfaction with their scar, cosmetic appearance, number of complications) will be analyzed using t-tests for independent groups. If time-to-healing is not distributed normally, or if there are censored observations (e.g., loss to follow-up, or not all patients have healed by the 16-week endpoint), a log-rank test will be used to test for differences in

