## Study Title: Prospective randomized clinical trial comparing outcomes of secondary intention wound care methods

healing time instead of a t-test. Time to healing in both groups will be plotted using Kaplan-Meier curves. The proportion of treatment failures in each group will be compared using chi-square or exact tests, as appropriate. Exploratory subgroup analysis for the above outcomes stratified by anatomic site, will be performed to assess for between-group differences across wound location. All tests will be two-sided with  $\alpha=0.05$ . Data will be analyzed using at Tufts CTSI using SAS or R software.

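### The 0–10 pain score has no planned analysis: pain enters only an undefined complication count, which cannot show whether one arm hurts more

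*Combined protocol and SAP*

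**What the plan says.** Four places in the combined protocol and SAP bear on this.

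- **Collection.** The Notes under Study Design / Procedures say that "The following information will be recorded for each patient at each clinic visit for both treatment arms", and the list begins "Date of follow up; pain (0/10); episodes of bleeding (# and whether mild, moderate, or severe". Pain is thus a graded score, repeated over follow-up. The Notes do not say whether it is taken before or after debridement at the visit.
- **Expectation.** Potential Risks and Discomforts gives as an example that "patients in the aggressive debridement group may experience more bleeding, pain, and scarring than the minimal debridement group".
- **Outcome.** Outcome Measures lists pain only as an item in the secondary outcome "number of complications (including pain, bleeding, infection, tumor recurrence) by time of complete healing or by week 16".
- **Analysis.** The Analytic Plan says that "continuous secondary outcomes (patient satisfaction with their scar, cosmetic appearance, number of complications) will be analyzed using t-tests for independent groups". It names no mean, peak, change or repeated-measures summary of pain.

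No section says what score makes pain a complication, whether it counts once per patient or once per visit, or how the four kinds of complication are combined. Visits are weekly in the aggressive arm and every two weeks in the minimal arm.

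**The concern.** A 0–10 score is not an event. To enter a number of complications it must be cut at some level, which discards intensity, and then be pooled with bleeding, infection and recurrence. The result answers a different question from whether one arm has more pain.

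That question matters here. The protocol describes both methods as accepted care at the site, so the trial informs a choice between them. One arm includes daily debridement at home, and the extra pain is part of what a patient would weigh against faster healing. The protocol foresees this harm and already measures it on a graded scale, yet the planned analysis yields no comparison attributable to it.

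**Working it through.** **Inputs from the documents.** 20 patients per arm; two-sided tests at 0.05; t-test on the number of complications; weekly against two-weekly visits. **Assumed, because the documents give none:** the size and SD of the pain difference, the cut-off, the counting unit and the rate of other complications.

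**1. The plan's own figure.** Sample Size/Power says: "To obtain 80% power to detect such a difference, assuming alpha=0.05 and a two-sided t-test, 20 patients per group (40 total) are required". With 14 days and SD 15, d = 14/15 = 0.933. The noncentral t calculation gives 19.03 per arm, rounded up to 20, with power 0.82 at 20. The figure reproduces, but it concerns healing time only.

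**2. Pain score tested directly.** For a 1 SD difference the noncentrality is 1 × √(20/2) = 3.16 on 38 df, and power is 87%. The difference detectable with 80% power is 0.91 SD.

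**3. Pain as one yes/no item per patient.** Cut midway between the arm means, the proportions are Φ(0.5) = 0.691 and 0.309. The difference is 0.383 and the variance in each arm is 0.691 × 0.309 = 0.213. Simulated power is about 67%.

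**4. The yes/no item plus other complications, equal between arms.** Let the others be Poisson with mean λ. The difference stays 0.383, the variance becomes 0.213 + λ, and the standardised difference is 0.383/√(0.213 + λ).

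| λ per patient | Standardised difference | Simulated power |
|---|---|---|
| 0.1 | 0.68 | about 57% |
| 0.3 | 0.53 | 40% |
| 0.7 | 0.40 | 24% |
| 1 | 0.35 | 19% |
| 2 | 0.26 | 13% |
| 4 | 0.19 | 9% |

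For a 0.75 SD difference the score has 64% power, the yes/no item 43%, and the count 13%, 9% and 7% at λ = 1, 2 and 4.

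**5. Other complications also higher in the aggressive arm.** With the model of step 4 and λ = 1, 2 and 4 in the minimal arm, a ratio of 1.5 gives rejection in 62%, 74% and 90% of runs; a ratio of 2 gives 91%, 99% and 100%. The signal is then mostly not pain. At λ = 4 and ratio 1.5 the other items contribute 0.5 × 4 = 2.0 to the difference in means, and pain contributes 0.383.

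**6. Pain counted at every visit.** Assume healing at mean 42 days, SD 15, in both arms, which gives about 6.5 visits against 3.5. Assume also a pain mean of 2 in the minimal arm, between-patient SD 1.6 and within-patient SD 1.2 (total √(2.56 + 1.44) = 2), and λ = 0.7 in both arms.

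| Cut-off | Mean count, no true pain difference | Rejection, no true difference | Rejection, true 2-point difference |
|---|---|---|---|
| ≥1 | 5.73 vs 3.41 | 88% | over 99% |
| ≥4 | 2.17 vs 1.50 | 17% | 99% |
| ≥7 | 0.78 vs 0.74 | 5% | 29% |

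At the two lower cut-offs the excess over 5% with no true difference comes from the visit schedule alone.

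**The case against.** A reader might infer that a large pain difference would probably be missed. The documents do not support that. It needs pain to count once per patient, which no section says, and other complications to be equal between arms, which sits badly with the risk section's own expectation of more bleeding as well as more pain. Steps 5 and 6 show that the count may well be significant when either condition fails. Even with three visits in each arm, pain counted at each, a within-patient correlation of 0.6 and equal other complications, power is 67%, 51% and 35% at λ = 1, 2 and 4, well above the once-per-patient figures. The size of the loss also depends on λ, for which the documents give no value.

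It can also be said that simple summing is only one reading of the outcome, that nothing forbids reporting each complication type or describing the pain scores, and that this is one component of one secondary outcome in a 40-patient trial powered for healing time. All of that stands, and it limits the severity. It does not remove the point. An unplanned description leaves the summary, time point and cut-off open until the data are seen, in a trial where patients and providers know the arm.

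**Conclusion.** The concern holds as a gap in the analysis plan. A predicted harm is measured on a 0–10 scale, no analysis of the score is named, and the rule that turns it into a counted complication is missing. Under each counting rule examined, the count does not reliably answer whether one arm hurts more. It dilutes pain (about 9% to 57% power against 87%, for a 1 SD difference counted once per patient with other complications equal), mixes it with other harms, or, counted per visit, can produce a difference from unequal attendance. Which of these would occur cannot be settled from the text, and the figures illustrate scenarios rather than forecast the result. The primary outcome is unaffected. The plan should be changed, because the remedy is cheap and the comparison matters to patients.

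**What to change.** - In Outcome Measures and the Analytic Plan, take pain out of the complication count and make the 0–10 score its own secondary outcome.
- Compare it only at visits both arms attend. Use week 2 as the main time point, or a mixed model over weeks 2, 4, 6 and so on that uses the available scores of patients who heal early. A simple mean of weeks 2 and 4 would need a rule for patients healed before week 4.
- Report the mean difference with its 95% confidence interval. For a single time point with 20 per arm the half-width is about 2.02 × √(2/20) = 0.64 SD.
- Have the form state whether pain is scored before or after debridement at the visit, the same way in both arms. Scoring before leaves out procedural pain and scoring after includes it; this is a choice for the investigators to make and state.
- Do not adjust for day-1 pain unless pain is added to the baseline items and taken before randomization. The Enrollment text collects baseline data after randomization and does not list pain.

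The cost is analysis wording and one line on the form, with no extra visits. The downsides are one more secondary comparison, and that later visits include only patients who are still unhealed.

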**Study Title: Prospective randomized clinical trial comparing outcomes of secondary intention wound care methods**

photographs for evaluation in 5 dimensions (pigmentation, vascularity, acceptability, observer comfort, and contour). "Observer comfort" measures the observer's "comfort level" when viewing the wound. The benefit of using this scale for the purposes of the study is because it is a photograph-based scale which can be evaluated later by a blinded physician rather than in the clinic at the time of the visit. The observer places a mark along the continuum and then that is measured from left to right and a corresponding score is given. The individual scores are tallied to obtain a single overall score ranging from "poor" to "excellent." It has been shown to have high observer reliability and internal consistency when evaluated by experts.

**Background Information / Significance / Scientific Rationale:**

Secondary intention is an established method of allowing post-surgical defects to heal. Previous studies have shown a positive association between the frequency of debridement and healing rates in chronic wounds, based on the belief that debridement initiates the first stage of wound healing, and transforms chronic wounds into acute wounds. However, the effect of debridement on acute, post-surgical wounds is not well-described in the literature.

 One retrospective review of debridement and time to heal did include the analysis of surgical wounds and concluded that frequent debridement led to shorter healing times, but no prospective studies have been done investigating whether this subset of wounds show a propensity to heal without frequent and aggressive debridement. Frequent debridement may unnecessarily strip the wound of macrophages, fibroblasts and keratinocytes that are valuable to wound healing in the acute, post-surgical wound. Additionally, while it is known that fibrin mediates many processes related to wound healing, it is not clear whether the presence of fibrin impedes or facilitates healing of the acute, post-surgical wound. Chronic wounds and wound care represent a major health burden in this country with significant associated costs. Through this study, we hope to assess whether frequent debridement facilitates or impedes acute wound healing. Lastly, findings of this study may have implications on the number and frequency of follow-up clinical visit for patients, with direct effects on costs on the healthcare system, opportunity costs to the patient, as well as the availability of those appointments for other uses. Optimizing wound care methods in this era of accountable care organizations (ACO) therefore targets the triple aim of improving patient satisfaction, improving quality of care, and reducing overall system costs.

**Study Title: Prospective randomized clinical trial comparing outcomes of secondary intention wound care methods**

**Participant Selection / Eligibility:**

Subjects

- 1) Dermatology patients at Lahey Clinic
  - 2) who have undergone Mohs surgery or excision
  - 3) who are older than 18 years
  - 4) who are able to give consent
  - 5) who had postoperative defects allowed to heal by secondary intention on the a) head and neck, b) trunk and upper extremities, c) lower extremities
  - 6) who are willing and able to return to clinic in Peabody for all wound care visits

Exclusion Criteria

- 1) Unable to consent (due to language barrier, mental status)
- 2) Unable to perform daily wound care
- 3) Unwilling or unable to return for follow-up
- 4) Have baseline venous stasis or pitting edema of the affected limb
- 5) Wear compression stockings or require use of a compressive bandage (such as an Unna Boot) at baseline.

**Subject Enrollment: / Consent Process / Screening / Randomization:**

Randomization

Block randomization using randomly-permuted block sizes of four and six will be used to ensure balanced enrollment in each arm as the trial progresses. Randomization will also be stratified by anatomic region. The three anatomic regions include: head and neck (5 per arm), trunk and upper extremity (5 per arm), and lower extremity (10 per arm). Randomization sequences will be generated in advance using an available web service and the list will be maintained by a research nurse not involved in patient enrollment. (Sealed Envelope Ltd. 2015. Create a blocked randomization list. [Online] Available from: <https://www.sealedenvelope.com/simple-randomiser/v1/lists> [Accessed 12 Oct 2015].) Treatment allocation assignment for each patient will be kept in sealed envelopes by the research nurse until after the patient is enrolled in the study. As patients are being enrolled, the clinician enrolling the patient will contact this research nurse to obtain the treatment assignment and will not have a priori knowledge of the randomization of the patient. In order to ensure a manageable caseload, only 10 patients will be enrolled in the study at any one time. Once 10

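### The protocol prints its block sizes and per-arm regional quotas, so a clinician who tracks earlier assignments can deduce a few upcoming ones with certainty

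*Combined protocol and SAP*

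**What the plan says.** The section on subject enrollment and randomization specifies the blocks: "Block randomization using randomly-permuted block sizes of four and six will be used to ensure balanced enrollment in each arm as the trial progresses". It adds "Randomization will also be stratified by anatomic region", with numbers for each region: "head and neck (5 per arm), trunk and upper extremity (5 per arm), and lower extremity (10 per arm"). These are regional totals of 10, 10 and 20.

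On concealment, the same section says that "the list will be maintained by a research nurse not involved in patient enrollment". That nurse keeps the assignments in sealed envelopes until the patient is enrolled, and the enrolling clinician, who must ask for each assignment, "will not have a priori knowledge of the randomization of the patient".

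Two other sections bear on this. Statistical Issues (Anticipated Limitations) concedes that "it will not be possible to conceal treatment arm to patients or providers". Participant Selection / Eligibility requires patients "who are willing and able to return to clinic in Peabody for all wound care visits", so all follow-up is at one clinic.

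The protocol does not say:
- that block sizes are withheld from enrollers;
- how the choice between four and six is made;
- what happens if a regional total falls inside a block or one arm fills first;
- whether the per-arm figures are targets or enforced caps.

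**The concern.** Envelopes and an independent list holder hide the list. They do not hide what can be worked out from the block sizes together with the assignments already made. Here the block sizes are in print, the strata are small, earlier assignments are visible to those giving care, and no more than 10 patients are on study at once. For some histories only one next assignment is possible.

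An enroller who knows the next arm can, without intending to, approach or defer a patient according to how quickly the wound is likely to heal. Stratification by region does not protect against selection within a region, and the planned primary comparison (t-test or log-rank) is unadjusted. What is at stake is a bias in time to healing, and a concealment statement that is stronger than the design supports.

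**Working it through.** **The plan's own figure.** Inputs from Statistical Issues: difference 14 days, SD 15 days, two-sided alpha 0.05, power 80%. The normal approximation gives 2 × (1.960 + 0.842)² × 15²/14² = 18.0, rounded up to 19 per arm. The t-test has power 79.9% at 19 and 82.0% at 20, so the stated 20 per group reproduces. The quotas agree with it: 5 + 5 + 10 = 20.

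**Assumptions not in the documents.** Each block is size 4 or 6 with probability 1/2, independently. The observer knows both sizes and every earlier assignment in the region.

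**How an assignment becomes certain.** If the first four patients in a region split 3:1, the block cannot be a four, so it is a six and patients 5 and 6 are both determined. The probability is 1/2 × [2 × C(3,3) × C(3,1) / C(6,4)] = 1/2 × 6/15 = 0.20. If the first three all go to one arm (1/2 × 2/20 = 0.05), patient 4 is determined as well.

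**Expected number certain**, summing such histories exactly over every position:

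| | 10-patient region | 20-patient region | All 40 (2 × first + second) |
|---|---|---|---|
| List cut at the regional total | 0.60 | 1.17 | 2.4 (6%) |
| Per-arm quotas enforced | 1.76 | 2.30 | 5.8 (15%) |

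Under enforcement the last patient in every region is always certain, because only one arm has a place left.

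**Size of the bias from those assignments.** Suppose that, whenever the next arm is certain, the clinician steers wounds whose expected healing time differs by ±d days. If a fraction f of patients is affected, the arms differ by 2 × d × f. The documents give no value for d.
- d = 3: 2 × 3 × 2.4/40 = 0.36 days; enforced, 2 × 3 × 5.8/40 = 0.87 days.
- d = 2: 0.24 and 0.58 days. d = 5: 0.60 and 1.45 days.

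For scale, the standard error of the difference is 15 × √(2/20) = 4.7 days.

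**What does not depend on publication.** The best guess is right for 6.79 of 10 and 13.70 of 20 patients: (2 × 6.79 + 13.70)/40 = 68%, against 50% by chance. A person who does not know the block sizes and names whichever arm is behind in the region scores the same 6.79 and 13.70. The reason is that each block is balanced, so the arm behind in the region is the arm behind in the current block. At d = 3 this guessing gives 2 × 3 × (2 × 0.682 − 1) = 2.2 days.

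**Do the blocks deliver the quotas?** One four-block and one six-block per ten patients give 5:5 and 10:10 every time. With random draws, a 10-patient region ends 5:5 with probability 0.50 + 0.25 × (0.667 + 0.600)/2 + 0.25 × 0.600 = 0.808. The terms are 4 and 6 in either order, 4+4 followed by either size, and 6+6. The 20-patient region ends 10:10 with probability 0.775. All three quotas are met with probability 0.808² × 0.775 = 0.51. The worst overall split is 17:23, where t-test power is 81.2% against 82.0% at 20:20.

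**The case against.** The strongest reply is that the larger numbers do not belong to this defect. A reader might infer that printing the block sizes lets clinicians guess 68% of assignments and so exposes the trial to about 2.2 days of bias. That inference fails: the lagging-arm rule scores the same without knowing the block sizes. Those figures come from small blocks within regions with visible history. They also require a guesser who acts at every opportunity. This part of the reply stands in full.

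A reader might also infer that the quotas contradict the blocks. They do not: 4 + 6 = 10 fits exactly, and the 51% figure rests on a selection rule that the protocol does not state. What survives is that the quotas are not guaranteed if sizes are drawn at random, and that no rule covers an arm filling early.

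Third, the documents do not show that any enroller follows three regional sequences, or that enrollers and follow-up staff are the same people. Follow-up debridement may be done by a physician or a nurse. Openness makes such tracking possible, not established. The nurse-held list, sealed envelopes and mixed block sizes are real safeguards. Wound dimensions are recorded before any intervention and wound characteristics are compared between arms, so steering on size might be noticed, although no adjustment is planned. This limits the severity, but it does not remove the deducible assignments.

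**Conclusion.** The point holds in a limited form. Anyone who tracks a region's history with the printed block sizes in hand can foresee about 2.4 of 40 assignments with certainty, and about 5.8 of 40 if the per-arm quotas are enforced. The statement that the enroller has no prior knowledge is therefore not fully delivered. The bias attributable to those assignments is about 0.4 to 0.9 days at an assumed ±3 days of steering, less than a fifth of the standard error (0.87/4.7 = 0.18).

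This rests on equal chances of four and six, complete tracking within each region, and an assumed steering effect. The quota question is a gap in operating rules with negligible effect on power. It would go too far to say that allocation is unconcealed or that the trial is compromised. The change is worth making because it costs almost nothing and brings the design closer to its own concealment statement.

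**What to change.** 1. Take the block sizes out of the protocol that enrollers read and put them in a document held by the research nurse or the statistician.
2. Regenerate the list for patients not yet assigned, with block sizes that are not disclosed. Removing the text alone would not help anyone who has already read it.
3. State regional totals of 10, 10 and 20 in place of per-arm quotas, so that no assignment is forced by an arm filling up.

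The cost is a wording amendment and a new list, with no extra patients and no change to care. A region may end 6/4 or 11/9, as the present blocks already allow under random draws, or a little further from balance because part-used blocks are abandoned. The loss of power is trivial: 81.2% at 17:23 and 80.5% at 16:24 (same t-test calculation), against 82.0% at 20:20.

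The change removes the assignments that can be deduced. It does not remove the 68% guess rate open to anyone who watches which arm is behind, and the revised text should not claim that it does.
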